Expected outcomes of aim 2: This aim will collect existing EMR data among the patients identified in aim 1. We will investigate the patients’ pre-existing comorbidities (i.e.: cardiovascular, renal and liver disease and diabetes), prognostic tumor factors (derived from the population of PCORnet cancer registry tumor data tables i.e.: stage, grade nodal status, mitotic count and Ki-67 index) and the effect of these on the selection of multiple line therapies received. We will additionally examine the effect of these patient, clinical and tumor factors on outcomes pulled via targeted chart reviews i.e.: disease progression and overall survival.

AIM 3: To compare the effectiveness of PRRT regimens on outcomes of renal toxicity, disease progression, and patient-reported symptoms and HRQoL.

Expected outcomes of aim 3: We will complete a comparative effectiveness study of PRRT with or without administration of other systemic therapies (e.g.: everolimus). We will utilize the combined PRO’s gathered in aim 1 and EMR data mined in aim 2 (i.e.: predictors), to compare the effectiveness of various PRRT treatment combinations and sequences, on outcomes of reduced creatinine clearance (renal toxicity) and HRQoL and symptom burden. We will additionally examine the effect on disease

progression of embolization therapy and chemotherapy prior to/following PRRT. Exploring the effectiveness of these outcomes in grade 3 well differentiated NETs and lung NETs (current areas of controversy and under study respectively) will be greatly beneficial.

AIM 4: To disseminate lessons learned and expand enrollment of the prospective cohort to other interested PCORnet sites, patient advocate organizations, and to use the infrastructure developed to aid in the study of other rare diseases.

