- 2) **European Organization for Research and Treatment of Cancer - Quality of Life Questionnaire - Neuroendocrine Carcinoid Module (EORTC QLQ-GI.NET21)** The EORTC QLQ-C30 can be used in conjunction with the EORTC QLQ-GI.NET21 specific questionnaire, which comprises a total of 21 items: four single-item assessments relating to muscle and/or bone pain (MBP), body image (BI), information (INF) and sexual functioning (SX), together with 17 items organized into five proposed scales: endocrine symptoms (ED; three items), GI symptoms (GI; five items), treatment-related symptoms (TR; three items), social functioning (SF21; three items) and disease-related worries (DRW; three items). Responses to the QLQ-GINET21 will be linearly transformed to a 0-100 scale using EORTC guidelines, with higher scores reflecting more severe symptoms.

[Time Frame: Change in mean score across baseline, 6, 12, and 18 month time points.]

- 3) **Sequencing of treatment regimens from electronic medical records.** This will involve identifying which treatments a patient used during their follow-up, and also in what order they received treatment. Dates and types of therapy initiated will be pulled from each patients EMR in reference to the patient’s index date (date of diagnosis). We will also be asking patients about their treatments (self-reported) in the baseline survey to ascertain potential missed therapies in the EMR. We will be comparing the frequency (N) and proportion (%) of use of a variety of therapies (i.e.: SSAs, bevacizumab, cytotoxic chemotherapy, everolimus, Interferon alpha, embolization, PRRT, small molecule TKIs) and the effects of their ordering/sequencing on outcomes of symptom burden and HRQoL.

[Time Frame: Up to 5 years, baseline to end of follow-up]

- 4) **Renal function.** Glomerular filtration rate (GFR) is the best overall index of kidney function. Normal GFR declines with age, and varies according to sex, race and body size. We will calculate creatinine clearance loss [54] by combining individual level CDM and enrollment questionnaire data on sex, race, height, weight and serum creatinine mg/dl laboratory values at regular intervals before and after PRRT cycles until the end of follow-up.

[Time Frame: Change in eGFR from baseline to end of follow-up.]

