8.1. Aim 1 (Frequency of treatment regimens)

In this aim we will describe the frequencies of treatment regimens by line of therapy and multi-line sequences. Information from Aim 1 will also be used – with input from the Patient Advocacy Committee (PAC) and Clinician Group – to finalize the comparators for Aims 2 and 3.

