8.3. Aim 3 (Comparative effectiveness of PRRT regimens)

Comparators will be PRRT with vs. without administration of other systemic therapies and PRRT before vs. after embolization therapy and chemotherapy. Comparisons will be with respect to renal toxicity, disease progression, patient-reported symptoms, and HRQoL. Heterogeneity of treatment effects will be assessed for these comparators in subgroups defined by tumor grade and type (GEP or lung NETs).

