9. STATISTICAL ANALYSIS PLAN

9.1. General Statistical Approach

Continuous variables will be summarized using descriptive statistics such as mean, standard deviation, median, minimum and maximum. Categorical variables will be summarized by count and percentage. Group comparisons will be assessed using chi-squared or Fisher's exact tests for categorical variables, and an analysis of variance or Kruskal-Wallis tests for continuous variables where appropriate. Adjustment for covariates listed in Tables 2 and 3 will be explored for each analysis as needed to account for potential confounding effects. Time-dependent covariates will be incorporated to capture changes in covariates across time, as necessary. Inclusion of random effects to account for potential clustering of patients treated at the same study site will be explored. Depending on the rate and pattern of missing data, multiple imputation methods may be considered to account for data missing at random or attributable to non-ignorable drop-out [56]. Planned study outcomes are summarized in Table 4.

9.1.1. Aim 1

Mixed effects regression models will be utilized to assess changes in HRQoL and symptoms within and between groups (i.e.: different treatment regimens) over time. Random effects will be employed to account for the longitudinally correlated nature of repeated questionnaire measurements. Should completion of questionnaires deviate from the planned assessment time points, a spatial power covariance structure will be included to account for the unequal time spacing between assessments within a patient.

9.1.2. Aim 2

Multinomial logistic regression models will be used to identify which patient, clinical, and tumor characteristics (Table 2), and patient attitudes and beliefs (Table 3) influence selection of treatment regimens for each line of treatment. The conditional Cox regression model proposed by Prentice, Williams, and Peterson (PWP) will be used to simultaneously model the gap times between initial diagnosis and first progression and between subsequent progressions as a function of the prognostic factors of interest for progression-free survival. The baseline hazard is expected to differ for first-line therapy and for subsequent lines of therapy, thus event-specific estimates will be obtained. A robust sandwich estimator will be used to account for potential dependencies within patients. Overall survival will be evaluated using a Cox regression model.

9.1.3. Aim 3

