Statistical analyses for Aim 3 will mimic those outlined in Aims 1 and 2, but with a special interest in evaluating the effectiveness of PRRT regimens on each of the outcomes. PRRT regimens to be evaluated include: PRRT alone, PRRT ± other biological therapy, PRRT ± prior embolization. Additionally, the PRRT isotope used (^{177}Lu vs ^{90}Y) will be evaluated.

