The primary objective of Aim 2 is to evaluate the effect of common treatment sequences on progression-free survival. A lack of historical data on the frequency and number of different variations of treatment sequences, and progression-free survival (PFS) differences by treatment and line of treatment coupled with the likelihood treatment sequences will further differ between the 14 sites taking part in this study make *any realistic and meaningful* sample size and power calculations impossible. Analyses for this aim will be exploratory, and will leverage the use of time-varying covariates in combination with the conditional Cox regression model proposed by Prentice, Williams, and Peterson (PWP) as a means of addressing the heterogeneity evidenced in the data. However, to put into perspective potential PFS differences that may be detected between two treatments using purely hypothetical situations, the below table summarizes power achieved for varying combinations of median PFS differences and number of patients per treatment arm. Calculations are based on the following assumptions: 1:1 treatment allocation, 48 months of uniform accrual and 12 months of follow-up, no loss to follow-up or switching treatments, unadjusted for confounders, and using the Lakatos approximation for a two-sided log-rank test with a 5% significance level.

Table 6: Power determination for changes in median PFS

Median PFS		N Per Treatment Arm	Power
Treatment 1	Treatment 2		
12 months	24 months	45	0.79
		50	0.83
24 months	36 months	175	0.80
		190	0.83

9.2.3. Aim 3

The primary objective of Aim 3 is to evaluate renal toxicity associated with the administration of PRRT as measured by creatinine clearance loss over time. We are expecting 2 mL/min/1.73m² annual decline in creatinine clearance based on averaged long-term follow-up with the most common PRRT isotope 177-Lu [34]. The repeated measures design with 180 subjects and 1 within-subject factor (time: baseline, 6 months, 12 months, and 18 months) achieves 100% power to detect creatinine clearance loss of 2 mL/min/1.73m² by 6 months, 4 mL/min/1.73m² by 12 months and 6 mL/min/1.73m² by 18 months, when the Wilks' Lambda approximate F test is used with a significance level of 0.05, and assuming an

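### The Aim 3 renal power covers only a one-group test of no change in PRRT patients; it does not apply to the regimen comparisons that define the aim

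*Protocol*

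**What the plan says.** Section 2.1 words Aim 3 as a comparison: "To compare the effectiveness of PRRT regimens on outcomes of renal toxicity", among other outcomes. Section 8.3 names the contrasts: "Comparators will be PRRT with vs. without administration of other systemic therapies and PRRT before vs. after embolization therapy and chemotherapy". It lists renal toxicity among the outcomes to be compared. Section 9.1.3 adds: "PRRT regimens to be evaluated include: PRRT alone, PRRT ± other biological therapy, PRRT ± prior embolization".

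Section 9.2.3 states the primary objective differently, as to "evaluate renal toxicity associated with the administration of PRRT as measured by creatinine clearance loss over time". Its calculation has 180 subjects and time (0, 6, 12, 18 months) as the only factor. It reports 100% power at SD 5, 99% at SD 15, and 99.6% for Bonferroni-corrected tests between two time points.

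Section 7.1 item 4 says of the renal outcome: "Normal GFR declines with age, and varies according to sex, race and body size". It plans creatinine values "at regular intervals before and after PRRT cycles until the end of follow-up".

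Table 4 marks the Aim 3 primary renal row as powered, at 0, 6, 12 and 18 months. The renal contrasts by isotope and by tumor location and grade have their own rows, marked as not powered. The Section 8.3 regimen contrasts have no renal row.

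**The concern.** The sized question and the stated aim differ in two ways.

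First, the null of the sized test is zero change. Ageing, comorbidity and other treatments can all make creatinine clearance fall in a cohort followed for 18 months. A significant time effect shows that function fell. It does not show that PRRT caused the fall, or that the fall exceeds what these patients would have had anyway.

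Second, the aim is to compare regimens, and a one-group time effect says nothing about the precision of a regimen contrast. The quoted power hardly moves between SD 5 and SD 15, whereas the detectable regimen difference triples.

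At stake is what the study may claim about the kidney: toxicity attributed to PRRT on a test that cannot isolate it, or a finding of no regimen difference read against a power figure that belongs to another test.

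**Working it through.** **Inputs from the protocol.** 3,010 patients; 10% PRRT, about 300; 60% questionnaire response, about 180 (Sections 9.2 and 9.2.1). Losses of 2, 4 and 6 mL/min/1.73m² by 6, 12 and 18 months; SD 5 or 15; correlation 0.5; alpha 0.05 (Section 9.2.3). Expected decline 2 per year (same section).

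**Assumed.** The split of PRRT patients between two regimens; equal correlation between visits; 6-monthly values; no covariate or multiplicity adjustment.

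**Step 1: reproduce the stated power.** For the one-group Wilks test with equal correlation ρ, the noncentrality is λ = n·Σ(μᵢ − μ̄)² / [SD²(1 − ρ)], with 3 and n − 3 degrees of freedom. The means 0, −2, −4, −6 give Σ = 9 + 1 + 1 + 9 = 20.
- SD 5: λ = 180 × 20 / 12.5 = 288, power 100% (stated 100%).
- SD 15: λ = 180 × 20 / 112.5 = 32, power 99.9% (stated 99%).
- Paired test of a loss of 2 at 0.05/6, SD 5: 99.6% (stated 99.6%).

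Table 5 (SD 18) also reproduces under equal correlation: 100%, 98.4% and 84.8%, against the stated 100%, 98.3% and 84.3%. Under a lag-1 structure its last two rows would be 81% and 54%. Equal correlation is therefore the supported structure. The match confirms that Section 9.2.3 is a one-group test of no change over time.

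**Step 2: what that null lets through.** As an illustration, suppose PRRT has no renal effect and function falls only with age, at an assumed 0.5 or 1.0 per year (the protocol gives no rate). With n = 180 the same test is significant in 39% or 96% of studies at SD 5, and in 8% or 19% at SD 15. The size depends on the assumed rate; the direction follows from Section 7.1.

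**Step 3: the regimen contrast.** At visit times 0, 0.5, 1 and 1.5 years, Sxx = 1.25. The per-patient slope SD is √[SD²(1 − ρ)/Sxx], which is √(12.5/1.25) = 3.16 at SD 5 and three times that at SD 15. The difference detectable at 80% power, two-sided 5%, is 2.80 × slope SD × √(1/n₁ + 1/n₂). For 150/150 at SD 5: 2.80 × 3.16 × 0.1155 = 1.02.

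| PRRT patients (split) | SD 5, per year | SD 15, per year |
|---|---|---|
| 300 (150/150) | 1.02 | 3.07 |
| 300 (60/240) | 1.28 | 3.84 |
| 300 (30/270) | 1.70 | 5.11 |
| 180 (90/90) | 1.32 | 3.96 |
| 180 (45/135) | 1.52 | 4.57 |
| 180 (18/162) | 2.20 | 6.60 |

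The benchmark is the expected total decline of 2 per year. (The 2/4/6 pattern that Section 9.2.3 sizes is 4 per year; that mismatch is a separate matter.)

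**The case against.** Section 9.2.3 and Table 4 agree with each other. The section states a within-group objective, says openly that time is the only factor, and powers that objective. The Table 4 row names the same measure at the same times, so its Yes is true of that row. This stands: the entry is not false, but it does not tell a reader that it stops short of the comparison in Sections 2.1 and 8.3.

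A reader might infer that the between-regimen analysis is missing. It is not. Section 9.1.3 carries over the Aim 1 models, which assess change "within and between groups (i.e.: different treatment regimens) over time", and Section 9.3 adjusts for factors linked to treatment selection, including age and comorbidities.

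A reader might also infer that no before/after-PRRT contrast is powered. That depends on whether baseline precedes PRRT, which Section 9.2.3 does not say, so the charge cannot be made.

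Section 8.1 leaves it to Aim 1 results "to finalize the comparators for Aims 2 and 3". That explains why there is no single power figure. Section 9.2.2 faces a similar uncertainty for PFS, and there the protocol labels the analyses exploratory and gives a hypothetical range in Table 6. Table 6 does not oblige Aim 3 to have a range, but nothing comparable to the exploratory label is given for the renal contrasts.

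**Conclusion.** The point holds in a limited form. The 99-100% power belongs to a test of zero change within PRRT patients over 18 months. It does not apply to the regimen comparisons, and rejecting that null does not on its own establish PRRT toxicity.

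The tempting stronger conclusion, that Aim 3 is underpowered for the kidney, is not supported. At the planning SD of 5 and an even split, a regimen difference of 1.0 per year (300 patients) or 1.3 per year (180 patients) is detectable, well below the expected decline of 2 per year. At SD 15, which the protocol calls unreasonably high, the figures are 3.1 and 4.0, both above that decline. Longer follow-up helps: at 150/150 over 36 months they would be 0.43 at SD 5 and 1.30 at SD 15. A rare regimen hurts.

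All these figures rest on assumed splits, equal correlation 0.5 and unadjusted contrasts. The conclusion about attribution rests only on the protocol's own statement about ageing, not on the assumed ageing rates.

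**What to change.** In Section 9.2.3 and the Table 4 renal row, state that the quoted power covers within-PRRT decline over 18 months only, and that this decline alone will not be attributed to PRRT. Base conclusions about regimens on the adjusted between-regimen models already planned in Sections 9.1.1, 9.1.3 and 9.3. Label the Section 8.3 renal contrasts exploratory and give them a Table 4 row marked as not powered, as the isotope contrast has.

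A hypothetical range in the style of Table 6 is optional. If given, show SD 5 and SD 15 for several splits and follow-up lengths. Base it on PRRT patients with laboratory data (up to about 300) rather than the 180 expected to complete questionnaires.

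The cost is wording, plus a short calculation if the range is added; no new data or analysis is needed. The downside is a less favourable power statement for Aim 3, and any range would rest on assumed splits until the comparators are settled.

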PRRT represents a true breakthrough in treatment of NETs but many questions remain about sequencing of PRRT with other therapies. PRRT is a form of molecularly targeted therapy, the main goal of which is to selectively deliver a high dose of radiation to the tumor cells, thus limiting irradiation of normal tissues. Unfortunately, due to tubular reabsorption and intracellular trapping of the radionuclide, PRRT therapies can accumulate in the renal cortex inducing toxicity [30]. Proper kidney protection, with the co-infusion of positively charged amino acids, is mandatory. Whilst the radiation dose to the kidneys can be reduced with this pre-treatment, the kidney remains a dose limiting organ

[31] with a creatinine clearance loss of about 3.8% per year for ¹⁷⁷Lu-octreotate and 7.3% per year for ⁹⁰Y-DOTATOC [32]. Moreover, studies have demonstrated a higher and more persistent decline in creatinine clearance if risk factors for delayed renal toxicity are present, particularly long-standing and poorly controlled diabetes and hypertension [33, 34]. On January 26, 2018, the US Food and Drug Administration (FDA) approved Lutathera (¹⁷⁷Lu-DOTATATE), a radiolabeled somatostatin analog, for the treatment of adults with somatostatin receptor-positive GEP-NETs [35]. Lutathera, is the first radiopharmaceutical to be approved by the FDA for this patient population. We are likely to see an increase in the use of ¹⁷⁷Lu-DOTATATE outside specialist NET centers. Therefore, real-world data on variables that may influence patient reported outcomes (i.e.: toxicities and adverse effects) and risk of progression after PRRT in combination with other biological therapies, is much needed.

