- 5) **Adverse toxicities.** We will assess incident acute renal failure, dialysis and liver failure during study follow-up (from diagnosis codes in the CDM). The occurrence of these events will be compared in reference to the treatment regimens received.
[Time Frame: Up to 5 years]

Table 4: Overview of Primary and Secondary outcomes for NET-PRO by project aims

Primary or Secondary	Name of Outcome	Specific Measure(s)/ Instrument(s) to Be Used	Timepoints (mths)	PROMIS and/or Core Outcome Set ?	Powered Yes/No/NA
Aim 1					
Primary	Health related Quality of Life (HRQoL)	EORTC QLQ-C30 EORTC QLQ-GI.NET21	0, 6, 12, 18	Yes	Yes
Secondary	Symptom inventory	Norfolk Carcinoid Symptom Score [49] Norfolk Carcinoid Symptom Score [49]	0, 6, 12, 18	No	No
Secondary	Experiences of care	Physician communication, coordination and responsiveness of care [62]	0, 6, 12, 18	No	No
Aim 2					
Primary	Sequencing of treatment regimens	-	0-60	No	Yes
Secondary	Progression-free survival	Time to event (Categorization of stable disease, disease progression with no change in treatment, disease progression with changes in treatment, and indeterminate)	0-60	No	Yes
Secondary	Overall survival	Time to event	0-60	No	NA
Secondary	Adverse toxicities	Incident acute renal failure, dialysis and liver failure during follow-up	0-60	No	NA
Aim 3					
Primary	Renal function	Creatinine clearance loss (per/Yr)	0, 6, 12, 18	No	Yes
Secondary	Adverse toxicities	CDM diagnosis codes for acute renal failure, dialysis and liver failure during follow-up	Up to 60	No	No
Secondary	Health related Quality of Life (HRQoL)	Changes in HRQoL and symptom scores	0, 6, 12, 18	No	No
Secondary	Renal toxicity (creatinine clearance) by PRRT isotope	Creatinine clearance loss (per/Yr) 177Lu vs 90Y	Up to 60	No	No
Secondary	Renal toxicity of PRRT by primary tumor location & grade 3 disease	Creatinine clearance loss (per/Yr) GEP-NETs vs lung NETs and G3	Up to 60	No	No

NA: Not applicable

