9.2. Sample Size and Power

For this prospective analysis we will have an estimated sample size of 3,010 patients. The sample size is computed for the population with minimum representation in the total sample. 2019 rates of PRRT were 15% in this population. Using a conservative estimation of 10% PRRT administration, and erring on the side of caution, our sample size and power justification is based on approximately 300 subjects (excluding HRQoL questionnaire completion rates). By the law of the minimum, all other treatment subgroups with representation above 10% will yield greater sample size and consequently higher powers for the below-stated differences

9.2.1. Aim 1

The primary objective of Aim 1 is to evaluate changes in HRQoL over time for each treatment. Calculations are based on using the EORTC QLQ-C30 as the primary HRQoL measure. Conservatively

estimating PRRT to be administered in 10% of patients and further expecting a response rate of 60% in the study, we would expect the PRRT group may have approximately 180 patients with complete HRQoL data. Using a repeated measures design with 1 within-subject factor (time: baseline, 6 months, 12 months, and 18 months), the design achieves the following power (Table 5) to detect a time effect for the corresponding mean change. Calculations are based on assuming an autocorrelation of 0.5 between measurements, a standard deviation of 18, and using a Wilks' Lambda Approximate F Test with a 5% significance level. The power will be higher if PRRT administration amounts to more than 10% of the prospective population.

Table 5: Alternative power for changes in EORTC QLQ-C30 within PRRT treated subgroup

MEAN CHANGE IN HRQOL OUTCOMES AT BASELINE, 6, 12 AND 18 MONTHS (RANGE 0-100)*	DIFFERENCE IN MEAN HRQOL SCORE (OVER EACH TIME POINT)	POWER*
65, 62, 59, 56	3-3-3	100%
65, 63, 61, 59	2-2-2	98.3%
65, 63.5, 62, 60.5	1.5-1.5-1.5	84.3%

* THE POWER APPLIES EQUALLY TO POSITIVE OR NEGATIVE SCORING SCALES.

9.2.2. Aim 2

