autocorrelation of 0.5 from one time point to the next and a standard deviation of 5 mL/min/1.73m². Should the standard deviation become unreasonably high in the order of 15 mL/min/1.73m², our sample size is large enough to achieve 99% power under the same parameter settings. In order to test Bonferroni-corrected pairwise differences, the individual tests will achieve 99.6% power to detect a clearance loss of 2 mL/min/1.73m² between two time points. The Bonferroni-corrected tests will be set at a significance level of 0.05/6.

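### Section 9.2.3 expects a renal decline of 2 mL/min/1.73m² per year but computes power for 4 per year; if the annual figure stands, the 99% power claimed at SD 15 is about 64%

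*Protocol*

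**What the plan says.** Section 9.2.3 (Aim 3) begins with the expected effect: "We are expecting 2 mL/min/1.73m² annual decline in creatinine clearance". It then says that 180 subjects seen at baseline, 6, 12 and 18 months give 100% power to "detect creatinine clearance loss of 2 mL/min/1.73m² by 6 months, 4 mL/min/1.73m² by 12 months and 6 mL/min/1.73m² by 18 months". The test is the Wilks' Lambda approximate F test at the 5% level, with an "autocorrelation of 0.5 from one time point to the next and a standard deviation of 5 mL/min/1.73m²".

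Two further statements rest on the same set-up:

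- If the SD rises to about 15, which the section itself calls unreasonably high, "our sample size is large enough to achieve 99% power under the same parameter settings".
- For the pairwise comparisons at 0.05/6, "the individual tests will achieve 99.6% power to detect a clearance loss of 2 mL/min/1.73m² between two time points".

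Table 4 lists renal function as the Aim 3 primary outcome, expresses it as a loss per year and marks it as powered.

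**The concern.** A steady loss of 2 per year amounts to 1, 2 and 3 by 6, 12 and 18 months. The pattern used for power, 2, 4 and 6, is 4 per year. No sentence explains the doubling or presents the larger loss as a deliberately chosen detectable difference.

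The annual rate is the quantity that Table 4 reports, so a reader needs to know which rate the study is powered for. The SD 15 sentence is there only to assure the reader that the sample suffices if variability is worse than planned. If the smaller rate is the expected one, that assurance was computed for twice the expected effect.

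A second, smaller point concerns the correlation. The phrase about one time point to the next reads as correlation that fades with distance. Section 9.2.1 words the same value without that restriction: "Calculations are based on assuming an autocorrelation of 0.5 between measurements, a standard deviation of 18". The two structures give clearly different powers at SD 15.

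**Working it through.** **Inputs (sections 9.2.1 and 9.2.3).** n = 180; four visits; correlation ρ = 0.5; SD σ = 5, or 15 in the pessimistic case; α = 0.05 overall and 0.05/6 pairwise. Table 5 uses the same design with σ = 18.

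**Overall test.** For one group the Wilks test is Hotelling's T². Power is P[F′(3, n−3; λ) > F₀.₉₅(3, n−3)], with λ = n·d′(CΣC′)⁻¹d. Here C takes successive differences, d holds the mean changes between adjacent visits, and Σ is the covariance matrix of the four visits. For n = 180 the critical value F₀.₉₅(3, 177) is 2.656.

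For a linear decline of s per visit and a constant correlation this reduces to λ = n·5s²/[σ²(1−ρ)] = 10ns²/σ² at ρ = 0.5. The 5 is the sum of squared deviations of visits 0, 1, 2, 3 from their mean.

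**Step 1: reproduce the stated figures.** AR(1) means correlation 0.5 between adjacent visits, fading with distance.

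| Case | λ, constant | Power, constant 0.5 | Power, AR(1) 0.5 | Stated |
|---|---|---|---|---|
| Table 5, s = 3, SD 18 | 16200/324 = 50.0 | >99.9% | 99.4% | 100% |
| Table 5, s = 2, SD 18 | 7200/324 = 22.2 | 98.4% | 81.3% | 98.3% |
| Table 5, s = 1.5, SD 18 | 4050/324 = 12.5 | 84.8% | 54.1% | 84.3% |
| Aim 3, 2/4/6, SD 5 | 7200/25 = 288 | ≈100% | ≈100% | 100% |
| Aim 3, 2/4/6, SD 15 | 7200/225 = 32 | 99.9% | 93.7% | 99% |

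Constant correlation reproduces Table 5 to within half a point and agrees with the SD 15 figure. AR(1) does not. The SD 5 figure cannot tell the two apart. The stated powers therefore belong to 2/4/6 with correlation 0.5 between every pair of visits.

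**Step 2: put in 2 per year (1/2/3, s = 1).**

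| SD | λ, constant | Power, constant 0.5 | Power, AR(1) 0.5 |
|---|---|---|---|
| 5 | 1800/25 = 72 | >99.9% | 99.97% |
| 10 | 1800/100 = 18 | 95% | 72% |
| 15 | 1800/225 = 8 | 64% | 36% |

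Power drops below 80% once the SD passes 12.7 (9.1 under AR(1)). Using n−1 or n−3 in place of n in λ moves the 64% only between 63.5% and 64.3%.

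**Step 3: pairwise tests.** Paired t at two-sided 0.05/6, with noncentrality Δ√n/[σ√(2(1−r))] and critical value 2.668 on 179 df. At σ = 5 and r = 0.5 the denominator is 5. A loss of 2 gives 2 × 13.416/5 = 5.37 and power 99.6%, exactly as stated. With 1/2/3 the six visit pairs split as follows:

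| Gap | Pairs | Loss | Power, constant 0.5 | Power, AR(1) 0.5 |
|---|---|---|---|---|
| 6 months | 3 | 1 | 51% | 51% |
| 12 months | 2 | 2 | 99.6% | 95.6% |
| 18 months | 1 | 3 | >99.9% | 99.96% |

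**Step 4: can the protocol settle which rate is meant?** Section 1.1.3 describes ¹⁷⁷Lu treatment "with a creatinine clearance loss of about 3.8% per year". That equals 2 mL per year at a baseline of 2/0.038 = 52.6, and 4 mL per year at 4/0.038 = 105.3. No baseline clearance is stated, so the percentage does not decide between them.

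**The case against.** The strongest reply is that the planning conclusion does not move. At SD 5 the power stays above 99.9% with 1/2/3, and at twice that SD it is still 95%. The 64% needs two conditions: that 2 per year is the intended rate, and that the SD is three times the planning value. If 4 per year was meant, every stated power stands and only one sentence is wrong. All of this is correct, and it limits the weight of the point.

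The inputs are also cautious. Under 1/2/3 with SD 15 and constant correlation, n = 300 (10% on PRRT, no reduction for questionnaire response) gives 88%, and n = 271 (3,010 × 0.15 × 0.60) gives 84%. These need laboratory values at all four times, which the protocol does not establish, and both remain below 99%. A one-degree-of-freedom test of the linear slope at n = 180 would reach about 80%. That is a different test from the one on which section 9.2.3 bases its power.

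The 99.6% is correct as worded, since the sentence names no visit gap. It becomes misleading only if it is applied to adjacent visits under the lower rate. AR(1) is not what was computed, so the correlation point is one of wording.

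None of these replies explains why the expected decline and the powered decline differ by a factor of two.

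**Conclusion.** The contradiction stands: section 9.2.3 expects 2 mL/min/1.73m² per year and computes power for 4. The protocol does not show which is the slip.

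If 2 per year is intended, the SD 15 claim falls from 99% to about 64%, and 99.6% does not hold for the three adjacent-visit pairs, where power is 51%. If 4 per year is intended, the powers are right and the statement of the expected decline is wrong. In both cases Aim 3 remains adequately powered at the planning SD of 5, so this should be fixed but does not threaten the sample size.

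The 64% and 51% assume a linear decline, 180 patients with complete data at four visits, the protocol's own tests, and correlation 0.5 between every pair of visits.

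**What to change.** Reconcile the expected annual decline with the 2/4/6 pattern, in one of two ways.

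- **If 2 per year stands:** replace 2/4/6 with 1/2/3. State power above 99.9% at SD 5 and 95% at SD 10, and replace the 99% at SD 15 with about 64%. Give pairwise power by visit gap: 51% at 6 months, 99.6% at 12 and above 99.9% at 18.
- **If 4 per year is intended:** keep the powers, and correct the expected-decline sentence and its justification.

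In both cases name the correlation structure. If the calculation used 0.5 between every pair of visits, say so. If fading correlation is meant, use the AR(1) figures throughout; with 1/2/3 these are 72% at SD 10, 36% at SD 15, and 51%, 95.6% and 99.96% for the three gaps.

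Optionally, state why n = 180 applies here. It carries over the 60% questionnaire response from Aim 1, although serum creatinine is a laboratory value.

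The cost is rewording one paragraph. No new data or patients are needed, but the stated power becomes less favourable if the annual figure is kept.
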